4.4. All Subjects with a Withdrawal Phase Longer than 90 Days

From all 273 subjects starting the Withdrawal phase after the week 68 visit (randomized subjects only, study groups **3a** and **3b**), those subjects will be selected who stay in the Withdrawal phase for more than 90 days after the last randomized verum dose of guselkumab. The subjects included in this analysis set will be evaluated for AEs in the study period starting from the 91st day after last verum dose in Study Part 2 until the day before re-treatment is started (if at all).

4.5. All Subjects who Started Re-Treatment

From all 273 subjects starting the Withdrawal phase after the week 68 visit (randomized subjects only), those 227 subjects will be selected who started re-treatment with open-label guselkumab for additional up to 3 doses after showing PASI deterioration of > 5 until the week 220 visit. In addition, 9 subjects started re-treatment without a Withdrawal phase (among these, 3 subjects who started re-treatment during Study Part 2 (before the week 68 visit) with PASI > 5, and 6 subjects who started re-treatment at the week 68 visit with a PASI value of 3 to 5) and will be included as well. The 236 subjects included in this analysis set will be evaluated for AEs starting from the date of re-treatment until the end of documentation.

5. STATISTICAL ANALYSES FOR THE OVERALL SAFETY ANALYSIS

As no efficacy data will be evaluated in the Overall safety analysis, no inferential statistics (ie, exploratory p-values, confidence intervals, etc.) will be provided; the analysis is purely descriptive. The statistical analysis will be performed using the SAS® software.

5.1. General Considerations

Descriptive statistics will include counts and proportions for categorical data, and mean, standard deviation, median, interquartile range, and range, for continuous data (if at all). Graphical data displays will not be generated.

In general, summary tables will be displayed by analysis group as the main classification variable and for the total of the sample in the respective analysis set. Individual subject data listings will be presented parameter-wise and will be sorted by analysis group, study site, subject's identification number, and date of AE onset. A more detailed description of the planned statistical analyses is provided in the sections below.

5.1.1. Visit Windows

Visit windows are not applicable for this analysis.

5.1.2. Pooling Algorithm for Analysis Centers

No pooling of centers will be performed.

5.1.3. Study Day and Relative Day

Study Day 1 or Day 1 refers to the start of the first study agent administration within Study Part 1. To all AEs a day relative to this date will be assigned.

Study day or relative day for the AE onset is defined as:

- AE start date – Date of Study Day 1 +1, if the AE start date is \geq date of Day 1
- AE start date – Date of Study Day 1, if the AE start date is $<$ date of Day 1.

There is no 'Day 0'.

5.1.4. Baseline and Endpoint

The terms "Baseline" and "Endpoint" are not defined in this analysis.

5.1.5. Imputation Rules for Missing AE Date/Time of Onset/Resolution

Partial onset dates of AEs will be imputed as follows:

- If the onset date of an AE is missing day only, it will be set to:
 - First day of the month that the AE occurred, if month/year of the onset of AE is different than the month/year of the study agent start
 - Day of study agent start, if the month/year of the onset of AE is the same as month/year of the study agent start date and month/year of the AE resolution date is different
 - Day of study agent start or day of AE resolution date, whichever is earliest, if month/year of the onset of AE and month/year of the study agent start date and month/year of the AE resolution date are same.
- If the onset date of an AE is missing both day and month, it will be set to the earliest of:
 - January 1 of the year of onset, as long as this date is on or after the study agent start date
 - Month and day of the [study agent start date], if this date is the same year that the AE occurred
 - Last day of the year if the year of the AE onset is prior to the year of the [study agent start date],
 - The AE resolution date.
- Completely missing onset dates will not be imputed.

Partial AE resolution dates not marked as ongoing will be imputed as follows:

- If the resolution date of an adverse event is missing day only, it will be set to the earliest of the last day of the month of occurrence of resolution or the day of the date of death, if the death occurred in that month.
- If the resolution date of an adverse event is missing both day and month, it will be set to the earliest of December 31 of the year or the day and month of the date of death, if the death occurred in that year.

- Completely missing resolution dates will not be imputed.

5.1.6. Treatment Failure Criteria

No treatment failure criteria are defined for this analysis.

5.1.7. Treatment Failure Rules

NA

5.1.8. Missing Data Imputation

There are no missing data in this analysis. All AEs documented will be considered for analysis.

5.2. Participant Dispositions

Data on subject disposition or demographic data will not be evaluated in this analysis.

5.3. Efficacy Analyses

Efficacy is not a topic of this analysis.

5.4. Safety Analyses

All safety analyses will be based on all five analysis sets introduced in chapter 4.

5.4.1. Adverse Events

The verbatim terms used in the eCRF by investigators to describe adverse events (AEs) are coded using the Medical Dictionary for Regulatory Activities (MedDRA). For analysis, AEs will be summarized by MedDRA system organ class (SOC) and Preferred Terms (PT) for each analysis group and overall.

For each analysis set, a separate time period will be considered for analysis:

Analysis set	Time period to be analyzed	Excluded time period
All subjects treated in Study Part 1 (N = 880)	Date of first dose (week 0) until study end	Date of week 28 dose and thereafter
All subjects treated in Study Part 2 (N = 822) #	Date of first verum dose (week 28 or week 36) until Date of last verum dose (week 52 or week 60) in Study Part 2 plus 90 days	Date of re-treatment and thereafter
All subjects randomized for Study Part 2 (N = 297) §	Date of randomization (week 28) until Date of last verum dose (week 52 or week 60) in Study Part 2 plus 90 days	Date of re-treatment and thereafter
All subjects with a Withdrawal phase longer than 90 days (N < 273)	91 st day after last verum dose in Study Part 2 until the day before re-	Date of re-treatment and thereafter

Analysis set	Time period to be analyzed	Excluded time period
	treatment is started (or study end if no re-treatment was started)	
All subjects who started re-treatment (N = 236)	Date of first re-treatment dose (week R0) until study end	None

In this analysis, subjects will be evaluated as well by analysis groups (super responders and non-super-responders).

§ In this analysis, subjects will be evaluated only by analysis groups (treated q8w and treated q16w).

If the AE onset date is recorded partially only or is completely missing, then the event will be considered for analysis unless it is known to be prior to the respective time period based on partial onset date or resolution date. Rules to impute a partial or missing onset date are presented in Section 5.1.5. In case a subject missed the week 68 visit, the date of the week 68 visit will be estimated as 8 weeks (56 days) after the week 60 visit.

For each AE, the number and percentage of subjects who experience at least one occurrence of the given event (SOC, PT) will be summarized by analysis group and overall. Summary tabulation will also provide the number of events, if applicable.

Summary tables will be provided – separately for each analysis set – for:

- AEs
- AEs by highest relationship to study agent
- AEs by worst severity
- Infections
- Injection site reactions
- Serious AEs (SAEs)
- Serious infections.

In addition to the summary tables, listings will be provided for subjects who

- had AEs
- had SAEs.

Deaths will be displayed by analysis group. Frequencies for the following parameters will be included in the summary table:

- Number of subjects who died
- Cause of death
- Relationship to study agent (yes/no) (yes includes the following eCRF items: possible, probable, very likely).

A listing of subjects who died will also be provided.

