The Investigator may continue treatment with guselkumab or switch to another commercially available treatment. Due to the half-life of guselkumab, it is recommended not to start a new therapy other than commercially available guselkumab during safety follow-up period. If the investigator feels strongly that another therapy is needed, this should be discussed with the sponsor before initiation of the new therapy.

Study Part 1:

Intervention Name	Guselkumab
Dose Formulation	A prefilled syringe assembled with the UltraSafe Plus™ Passive Needle Guard (PFS-U) device, designed to deliver a single, fixed dose of 100 mg guselkumab
Unit Dose Strength(s)	100mg
Dosage Level(s)	100mg at Weeks 0, 4, 12 and 20
Route of Administration	Subcutaneous

Study Part 2:-

Group Name	Group 2a (SRe with PASI score=0) at Week 20 and 28	Group 2b (SRe with PASI score=0) at Week 20 and 28	Group 2c (non-SRe with a PASI score>0) at Week 20 and/or Week 28
Intervention Name	Guselkumab (blinded)	Guselkumab and Matching placebo (blinded)	Guselkumab (open label)
Dose Formulation	A prefilled syringe assembled with the UltraSafe Plus™ Passive Needle Guard (PFS-U) device, designed to deliver a single, fixed dose of guselkumab 100 mg	A prefilled syringe assembled with the UltraSafe Plus™ Passive Needle Guard (PFS-U) device, designed to deliver a single, fixed dose of guselkumab 100 mg and matching placebo	A prefilled syringe assembled with the UltraSafe Plus™ Passive Needle Guard (PFS-U) device, designed to deliver a single, fixed dose of guselkumab 100 mg
Unit Dose Strength(s)	100mg	100mg	100mg
Dosage Level(s)	100 mg q8w at weeks 28/36/44/52/60	100mg q16w at weeks 36 and 52 and matching placebo at weeks 28/44/60	100 mg q8w at weeks 28/36/44/52/60
Route of Administration	subcutaneous	subcutaneous	subcutaneous

Study Part 3

Subjects of groups 2a and 2b with a PASI score <3 at week 68 will be withdrawn from the study medication and will be observed until W220 or until loss of disease control, whereupon patients are re-treated.

Retreatment Phase (Subjects of groups 2a,2b, 3a and 3b losing control of disease, defined as PASI score >5 at any visit of Study Parts 2 or 3 [ie, until week 220]). Exception: patients with PASI ≥ 3 at week 68 received re-treatment.

Group Name	Retreatment Groups 2d and 3c
	SRe with fluctuating disease at week 68 (PASI ≥ 3) or with loss of disease control (PASI > 5) at any other visit after week 28 (group 2d) / after week 68 (group 3c)
Intervention Name	Guselkumab

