In addition to above analyses, safety aspects need to be evaluated using the adverse event (AE) data from the entire study period. This current SAP describes the statistical analyses planned to be performed for this purpose and should be read in conjunction with the CSP and the electronic Case Report Form (eCRF).

This plan is the core document for all statistical programming planned for the Overall safety analysis of study protocol no. CNTO1959PSO3012. The statistical analysis will focus on the comparison of adverse event data in various subgroups.

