4. POPULATIONS (ANALYSIS SETS) FOR THE OVERALL SAFETY ANALYSIS

In the Overall safety analysis, the following analysis sets will be defined.

4.1. All Subjects Treated in Study Part 1

880 subjects started open-label guselkumab in Study Part 1 and received at least one dose (study group **1**). All 880 subjects are included in this analysis set to be evaluated for AEs in the study period from date of first dose (week 0) until the day before the date of the week 28 dose (start of randomized or open-label treatment within Study Part 2), or, in 58 subjects not starting Study Part 2, until the end of documentation.

4.2. All Subjects Treated in Study Part 2

From all 880 subjects who started open-label guselkumab in Study Part 1, 297 super-responders received randomized treatment in Study Part 2 (study groups **2a** and **2b**) and 525 non-super-responders continued open-label treatment (study group **2c**). So, 822 subjects are included in this analysis set and will be displayed separately to be evaluated for AEs in the study period from date

of the first verum dose (week 28 or week 36) until date of last verum dose (week 52 or week 60) in Study Part 2 plus 90 days (date of re-treatment and thereafter excluded, if at all).

4.3. All Subjects Randomized for Study Part 2

Among the 297 super-responders treated in Study Part 2 (study groups **2a** and **2b**), 148 were randomized to guselkumab q8w and 149 to guselkumab q16w. The 297 subjects included in this analysis set will be evaluated and displayed separately for AEs in the study period from date of randomization (week 28) until date of last verum dose (week 52 or week 60) in Part 2 plus 90 days (date of re-treatment and thereafter excluded, if at all).

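### Overall safety SAP, set 4.2: the super-responder column pools q8w and q16w, so its nominal AE window is about 16% shorter than that of the all-q8w non-super-responders beside it

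*SAP*

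**What the plan says.** The Introduction of the overall safety SAP states its purpose: "The statistical analysis will focus on the comparison of adverse event data in various subgroups".

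Section 4.2 defines the set treated in Study Part 2. In it, "297 super-responders received randomized treatment in Study Part 2" and "525 non-super-responders continued open-label treatment", 822 subjects in all. Section 4.3 gives the regimen split of the super-responders: "148 were randomized to guselkumab q8w and 149 to guselkumab q16w".

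For set 4.2, the table in Section 5.4.1 opens the AE period at "Date of first verum dose (week 28 or week 36") and closes it 90 days after the last active dose of Part 2 (week 52 or week 60). Anything from re-treatment onward is excluded. The footnote on columns reads: "In this analysis, subjects will be evaluated as well by analysis groups (super responders and non-super-responders". The q8w/q16w split is footnoted only for set 4.3.

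The measure is the number and percentage of subjects with at least one event, with event counts where applicable. Section 6.7 leaves exposure out of the analysis, and Section 5.4.3 plans no further subgroups.

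Protocol Section 6 gives the schedules. Groups 2a and 2c receive active drug at weeks 28, 36, 44, 52 and 60. Group 2b receives "100mg q16w at weeks 36 and 52 and matching placebo at weeks 28/44/60".

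**The concern.** The AE period is tied to active dosing, so its length depends on the regimen. About half of the super-responder column is on q16w, with a later start and an earlier end. Nobody in the non-super-responder column is on q16w. A crude percentage takes no account of this, so the column with less observation time tends to show fewer subjects with events even where the daily risk is the same. The same holds for infections and serious AEs, which are tabulated in the same way.

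The pooled column also mixes two things that a reader would want to keep apart: being a super-responder, and being dosed half as often. Within this SAP, set 4.2 is the only table that places super-responders beside non-super-responders. At stake is the interpretation of that one descriptive contrast. The confirmatory result is not affected.

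**Working it through.** **The plan's own counts.** 297 + 525 = 822, and 880 treated in Part 1 less 58 who did not start Part 2 = 822. The regimen split gives 148 + 149 = 297. All agree.

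**Nominal windows** = (week of last active dose − week of first active dose) × 7 + 90 days.

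| Group | n | Window (days) | Active injections |
|---|---|---|---|
| Super-responders q8w (2a) | 148 | (60 − 28) × 7 + 90 = 314 | 5 |
| Super-responders q16w (2b) | 149 | (52 − 36) × 7 + 90 = 202 | 2 |
| Non-super-responders q8w (2c) | 525 | 314, or 224 + 84 = 308 | 5 |

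The 308 applies because the last visit of group 2c is at week 72 (Protocol Section 3.1 and Time and Events Schedule), which is 84 days after the week 60 dose. The 314 applies only if events are documented for the full 90 days.

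**Pooled super-responder column.** (148 × 314 + 149 × 202) / 297 = 76,570 / 297 = 257.8 days.

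- Against 308 days: 1 − 257.8/308 = 16.3% shorter.
- Against 314 days: 1 − 257.8/314 = 17.9% shorter.

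**Injections inside the window.**

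- Active: (148 × 5 + 149 × 2) / 297 = 3.49 versus 5, or 30% fewer.
- Active plus placebo: a q16w subject has four injections in the window (weeks 36, 44, 52 and 60), so (148 × 5 + 149 × 4) / 297 = 4.50 versus 5, or 10% fewer.

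**Effect on a crude percentage.** The documents give no AE rate, so the incidences below are assumptions. Give every subject the same constant daily hazard *h*, set so that non-super-responders reach incidence *p* over their window *W*: h = −ln(1 − p)/W. The expected super-responder percentage is then [148 × (1 − exp(−314h)) + 149 × (1 − exp(−202h))] / 297.

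| Assumed *p*, non-super-responders | Super-responders, W = 308 | Super-responders, W = 314 | Shift (points) |
|---|---|---|---|
| 5% | 4.2% | 4.1% | −0.8 to −0.9 |
| 20% | 17.0% | 16.7% | −3.0 to −3.3 |
| 50% | 43.6% | 43.0% | −6.4 to −7.0 |

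**The case against.** **The analysis is descriptive.** It has no hypothesis, p-values or confidence intervals (Sections 2 and 5), and the protocol did not plan it. This stands, and it limits the weight of the point. But the SAP's declared focus is comparing AEs between groups, and with no rates shown the crude percentages are what a reader will compare.

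**The like-for-like column already exists.** For q8w super-responders, randomization and first active dose both fall at week 28 and the end rule is the same. The q8w column of set 4.3 therefore has the same nominal window as a q8w super-responder column in set 4.2 would have. This is true and makes the repair cheap. But set 4.3 holds randomized subjects only, so that column never stands beside group 2c, and the SAP does not tell the reader to compare across the two tables.

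**Person-time rates would keep all 297 super-responders.** They would deal with the window but not with the mixing of regimen and responder status.

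**A q8w-only comparison is still not clean.** Group 2a is blinded and group 2c open-label, and the groups are defined by response. Group 2c also takes subjects whose week 20 or week 28 efficacy assessment was not done on site (Protocol Section 6). All of this stands, so the comparison should be labelled non-randomized.

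Three stronger readings are tempting, and the documents do not support them.

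- *Super-responders will show fewer AEs.* This is only an expectation at equal constant hazards. The groups may truly differ in either direction, and the difference at low incidence is under one point.
- *The 30% fewer active injections are a further artefact.* They reflect a real dosing difference. It lowers AE counts only if AEs depend on dose, which no document states. For injection site reactions the relevant shortfall is about 10%, because placebo injections count too.
- *This is the trial's only comparison of super-responders with non-super-responders.* That holds within this SAP only. The Part 2 SAP is not among the documents, and Protocol Sections 11.7 and 11.9 plan AE summaries by treatment group and a Part 2 safety analysis from week 28 to week 68.

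**Conclusion.** The point holds as a moderate, cheaply avoided bias in one descriptive contrast. The nominal observation window of the pooled super-responder column is about 16% shorter than that of the non-super-responder column, and 18% is the outer bound. At equal underlying rates this pulls the super-responder percentages down, by an amount that grows with incidence over the range shown. The direction of the observed difference cannot be predicted. As the columns stand, that difference cannot be attributed to responder status.

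The window figures rest on scheduled doses. Early discontinuation by group is not given, so the realized gap is unknown. Exclusion from re-treatment onward affects few subjects (3 before week 68 and 6 at week 68, Section 4.5) and can only shorten the super-responder window further. The percentage shifts rest on the assumed incidences and on a common constant hazard.

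**What to change.** In Section 4.2 and in the set 4.2 footnote of Section 5.4.1 of the overall safety SAP:

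1. Show three columns: super-responders q8w, super-responders q16w, and non-super-responders q8w.
2. State that the responder-status comparison is super-responders q8w (n = 148) versus non-super-responders q8w (n = 525), and that it is descriptive and non-randomized. Both have five scheduled active doses, and the nominal windows are close (314 versus 308 to 314 days).
3. State that the pooled super-responder column is not to be used for that comparison.

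This costs some SAP wording and one extra column per set 4.2 table, from data already collected. The price is precision: 148 instead of 297 super-responders enter the comparison, so rare events are described less precisely.

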5.4.2. Additional Safety Assessments

No other safety parameters will be analyzed in the Overall safety analysis.

5.4.3. Definition of Subgroups

No subgroup analyses are planned for the Overall safety analysis. For each analysis set, analysis groups are defined in Chapter 4.

5.5. Interim Analyses

There will be no interim analysis for the Overall safety analysis.

6. SUPPORTING DOCUMENTATION

6.1. Appendix 1 List of Abbreviations

AE	Adverse event
CSP	Clinical Study Protocol
eCRF	electronic Case Report Form
FOIA	Freedom of Information Act
ICH	International Council for Harmonization
ie	that is
MedDRA	Medical Dictionary for Regulatory Activities
mg	Milligram
PSO	Psoriasis
q8w/q16w	every 8/16 weeks
SAE	Serious adverse event
SAP	Statistical Analysis Plan
SAS®	Statistical Analysis System
SOC	System organ class
SRe	Super-Responder

6.2. Appendix 2 Changes to Protocol-Planned Analyses

This analysis was not pre-planned per study protocol, it is introduced by this SAP.

6.3. Appendix 3 Demographics and Baseline Characteristics

Demographic and baseline characteristics are not part of this analysis. Respective data have already been shown in previous analyses.

6.4. Appendix 4 Protocol Deviations

Protocol deviations will not be considered for this analysis.

6.5. Appendix 5 Prior and Concomitant Medications

Prior and concomitant medications are not part of this analysis.

6.6. Appendix 6 Medical History

Medical history is not part of this analysis.

6.7. Appendix 7 Intervention Compliance

Exposure to study agent and study compliance are not part of this analysis..

6.8. Appendix 8 Adverse Events of Special Interest

Not applicable for this analysis.

6.9. Appendix 9 Medications of Special Interest

Not applicable for this analysis.

6.10. Appendix 10 Laboratory Toxicity Grading

Not applicable for this analysis.

1. INTRODUCTION

The statistical analysis plan (SAP) is a detailed technical extension to the Clinical Study Protocol (CSP) and follows the principles of the guideline ICH E9.

Statistical analyses of Janssen-Cilag GmbH CSP CNTO1959PSO3012 are performed for each of the three Study Parts (of which Parts 1 and 2 are already completed):

- The exploratory analysis of Study Part 1 (“Open-label treatment phase”) occurred after all subjects had completed their visit at week 28 (ie, 28 weeks after study inclusion) or discontinued earlier. This analysis included the safety analysis and all efficacy measures until the week 28 visit.
- The confirmatory analysis of this study was performed at the end of Study Part 2 (“Double-blind treatment phase”), ie, after all subjects had completed their visit at week 68 (ie, 40 weeks after randomization) or discontinued earlier. This analysis included the confirmatory analysis of the primary endpoint, and the exploratory analyses of the major secondary endpoints and all other predefined efficacy and safety analyses from week 28 until week 68).

The analyses of Study Part 3 (“Drug withdrawal phase”) will be exploratory and will occur after all subjects have completed, if not gone into re-treatment before, their visit at week 116 (ie, 48 weeks after inclusion in Study Part 3 at week 68), at week 164 (ie, 96 weeks after inclusion in Study Part 3 at week 68), and at week 220 (ie, 152 weeks after inclusion in Study Part 3 at week 68). Only subjects who started Study Part 3 in study groups 3a or 3b will be included in the analyses. These analyses will include the safety evaluations and all efficacy measures after week 68 and will cover the time until week 116/164/220, respectively. Thus, the statistical analysis for Study Part 3 will consist of two interim analyses and one final analysis. All three analyses are described in the current SAP.

Final decisions about which subjects are to be included in the analyses of the Study Parts 1, 2, or 3, are made during the Data Review or Dry Run Meetings.

This current SAP describes the statistical analyses planned to be performed for Study Part 3 and should be read in conjunction with the CSP and the electronic Case Report Form (eCRF). Statistical analyses of study data recorded before week 68 have been specified in separate SAPs, if not otherwise specified.

This plan is the core document for all statistical programming planned for the analyses of Study Part 3 of study protocol no. CNTO1959PSO3012. The statistical analyses will focus on the comparison of the two groups which were randomized for double-blind treatment in Study Part 2, ie, group **3a** (guselkumab 100 mg q8w in Study Part 2 but no treatment in Study Part 3) vs. group **3b** (guselkumab 100 mg q16w in Study Part 2 but no treatment in Study Part 3).

Note: Subjects losing control of disease, defined as PASI score >5 at any visit during Study Part 2 (ie, until week 68) or Study Part 3 (ie, until weeks 116, 164, or 220), and subjects with fluctuating disease (PASI score 3 to 5) at week 68 will enter the re-treatment-arms (**2d** or **3c**) with three guselkumab 100 mg administrations starting at that visit (= re-treatment week 0, followed by administration at re-treatment weeks 8 and 16). Statistical analyses of re-treatment study data will be specified in a separate SAP. Evaluating the endpoint related to the re-treatment phase in a separate analysis allows an earlier analysis of the endpoints measured in study groups 3a and 3b.

